#### **4.2.22.5 Additional Analyses of the Exploratory Endpoint #14**

Not Applicable

#### **4.2.22.6 Subgroup Analyses**

Not Applicable

### **4.2.23 Exploratory Endpoint #15 (Dialysis initiation)**

*Time to first occurrence of dialysis initiation at any time post-discharge up to 180 days in each arm.*

#### **4.2.23.1 Definition**

- Population: Full analysis set
- Endpoint: Time to first occurrence of dialysis initiation at any time post-discharge up to 180 days inclusive.
- Intercurrent event strategy: Participants who discontinue of treatment will continue to be followed up to the first use of dialysis post-discharge (treatment policy strategy). Participants who require rescue therapy for HK or have RAASi down-titration (including discontinuation) will continue to be followed up to the first use of dialysis post-discharge (treatment policy strategy). Participants who require any hospital admission or ED visit will continue to be followed up to the first use of dialysis post-discharge (treatment policy strategy). Participants who die of any cause will be censored at the date of death. Participants who are lost to follow-up will be censored at the date of loss to follow-up. Participants who do not have an event by 180 days post-discharge will be administratively censored at the date of 180 days post-discharge.

- Population level summary (analysis): Kaplan-Meier plots of the survival function for the SZC and SoC treatment groups will be presented. Log-rank test for testing will be used to calculate a two-sided p-value, Cox proportional hazards ratio for estimation, with randomised treatment group as the independent variable. The HR and the two-sided 95% confidence interval will be presented. The risk difference and two-sided 95% confidence interval will be presented (as per section 4.2.4.2) at 180 days post-discharge.

#### **4.2.23.2 Derivations**

Time to first occurrence will be defined as the earliest date of (dialysis initiation, date of death, loss to follow-up, date of 180 days post-discharge) – date of randomization + 1.

#### **4.2.23.3 Handling of Dropouts and Missing Data**

Participants who are lost to follow-up will be censored at the date of discontinuation as recorded on the participant's disposition form.

#### **4.2.23.4 Primary Analysis of Exploratory Endpoint #15**

The primary analysis for this exploratory endpoint will be conducted as per section 4.2.18.4.

#### **4.2.23.5 Additional Analyses of the Exploratory Endpoint #15**

The analysis will be repeated in the FAS using an alternative population level summary where the Cox proportional hazards model will include randomised treatment group and the following baseline variables: age (as a cubic spline), sex (female, male), participant recruitment country, presence of heart failure (yes/no), diabetes (yes/no), RAASi use (yes/no), CKD stage and baseline  $K^+$  (mild HK defined by  $5.0 < K^+ \leq 5.5$  and moderate/severe HK defined by  $5.5 < K^+ \leq 6.5$  mmol/L) as independent variables.

#### **4.2.23.6 Subgroup Analyses**

Not Applicable

#### **4.2.24 Exploratory Endpoint #16 (ICU admission)**

*Time to first occurrence of ICU admissions at any time post-discharge up to 180 days in each arm.*

##### **4.2.24.1 Definition**

- Population: Full analysis set
- Endpoint: Time to first occurrence of ICU admission at any time post-discharge up to 180 days inclusive.
- Intercurrent event strategy: Participants who discontinue of treatment will continue to be followed up to the first ICU admission post-discharge (treatment policy strategy). Participants who require rescue therapy for HK or who have RAASi down-titration

(including discontinuation) will continue to be followed up to the first ICU admission post-discharge (treatment policy strategy). Participants who require any hospital admission or ED visit will continue to be followed up to the first ICU admission post-discharge (treatment policy strategy). Participants who die of any cause will be censored at the date of death. Participants who are lost to follow-up will be censored at the date of loss to follow-up. Participants who do not have an event by 180 days post-discharge will be administratively censored at the date of 180 days post-discharge.

- Population level summary (analysis): Kaplan-Meier plots of the survival function for the SZC and SoC treatment groups will be presented. Log-rank test for testing will be used to calculate a two-sided p-value, Cox proportional hazards ratio for estimation, with randomised treatment group (reference level SoC) as the independent variable. The HR and the two-sided 95% confidence interval will be presented. The risk difference and two-sided 95% confidence interval will be presented.

#### **4.2.24.2 Derivations**

Time to first occurrence will be defined as the earliest date of (ICU admission, date of death, loss to follow-up, date of 180 days post-discharge) – date of randomization + 1.

#### **4.2.24.3 Handling of Dropouts and Missing Data**

Participants who are lost to follow-up will be censored at the date of discontinuation as recorded on the participant's disposition form.

#### **4.2.24.4 Primary Analysis of Exploratory Endpoint #16**

The primary analysis for this exploratory endpoint will be conducted as per section 4.2.18.4.

#### **4.2.24.5 Additional Analyses of the Exploratory Endpoint #16**

The analysis will be repeated in the FAS using an alternative population level summary where the Cox proportional hazards model will include randomised treatment group and the following baseline variables: age (as a cubic spline), sex (female, male), participant recruitment country, presence of heart failure (yes/no), diabetes (yes/no), RAASi use (yes/no), CKD stage and baseline  $K^+$  (mild HK defined by  $5.0 < K^+ \leq 5.5$  and moderate/severe HK defined by  $5.5 < K^+ \leq 6.5$  mmol/L) as independent variables.

#### **4.2.24.6 Subgroup Analyses**

Not Applicable.

### **4.2.25 Exploratory Endpoint #17 (RAASi use)**

*Use of RAASi at 90 and 180 days post-discharge by treatment arm.*

#### **4.2.25.1 Definition**

- Population: Full analysis set

- Endpoint: Number and proportion of participants on RAASI at discharge who remained on RAASI at days 90 and 180 post-discharge, respectively, by treatment arm. The number and proportion of participants on RAASI at discharge who have increased RAASI dose by 90 and 180 days post-discharge, respectively, by treatment arm. The number and proportion of participants on RAASI at discharge who have decreased RAASI dose by 90 and 180 days post-discharge, respectively, by treatment arm. The number and proportion of participants who have initiated RAASI by 90 and 180 days post-discharge respectively.
- Intercurrent event strategy: Participants who discontinue treatment, use rescue therapy for HK or require either hospitalisation or ED visits will have all available RAASI use data used irrespective of the intercurrent event (treatment policy strategy). Participants who experience all-cause death, or loss to follow-up prior to days 90 and 180 respectively will be excluded from the numerator and denominator of the analysis (while on treatment strategy).
- Population level summary: Number and proportion of participants on RAASI at discharge who remained on RAASI at 90 and 180 days post-discharge by treatment arm. Number and proportion of participants on RAASI at discharge who have increased RAASI dose by 90 and 180 days post-discharge by treatment arm. Number and proportion of participants on RAASI at discharge who have decreased RAASI dose by 90 and 180 days post-discharge by treatment arm. Number and proportion of participants who initiated RAASI by 90 and 180 days post-discharge by treatment arm.

#### 4.2.25.2 Derivations

RAASI use at discharge is derived using the concomitant medication rescue medications eCRF as where one or more CMCLASCD in ('C09AA', 'C09BA', 'C09BB', 'C09BX', 'C09CA', 'C09DA', 'C09DB', 'C09DX', 'C09XA') where Start Date is prior to the date of randomisation and End Date is ongoing or after the date of randomisation. RAASI use at day 90 post-discharge is derived using the concomitant medication rescue medications eCRF as above where Start Date is prior to day 90 post-discharge and End Date is ongoing or after day 90 post-discharge. RAASI use at day 180 post-discharge is derived using the concomitant medication rescue medications eCRF as above where Start Date is prior to day 180 post-discharge and End Date is ongoing or after day 180 post-discharge. A RAASI dose increase at 90 and 180 days post-discharge is defined where the CMDECOD at discharge is different at 90 or 180 days or where CMDECOD at 90 or 180 matches that at discharge but the CMDOSTXT is greater than at discharge. A RAASI dose decrease at 90 and 180 days post-discharge is defined, where CMDECOD at 90 or 180 days matches that at discharge but the CMDOSTXT is less than at discharge.

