- Participants currently receiving any treatment for the current episode of HK and are already NK at baseline ($\text{K}^+ \leq 5.0 \text{ mmol/L}$): 1) stop any

current K-binder, 2) start SZC maintenance dose (note: participants currently on SZC maintenance dose should continue SZC maintenance dose).

- All treatment decisions, including modification to the ongoing therapy for HK, must be based on the investigator's medical judgement of the participant's best interest.

Typically, NK is achieved within 24 to 48 hours. If participants are still hyperkalaemic after 48 hours of treatment, the same regimen can be continued for an additional 24 hours. If NK is not achieved after 72 hours of treatment, other treatment approaches should be considered, and the participant discontinued from the study.

Participants reaching NK (K^+ between 3.5 and 5.0 mmol/L, inclusive) within 72 hours will be started on maintenance dose of SZC until discharge.

Discharge visit: The day they get discharged from the hospital, participants will be randomised to one of the 2 parallel arms at this visit and enter the outpatient phase. To be randomised, participants have to be NK (K^+ between 3.5 and 5.0 mmol/L, inclusive) and should be started on a maintenance dose for SZC. The discharge visit will take place 1 to 21 days after the baseline visit. Medical monitor's approval may be sought for allowing longer duration hospital stays for specific participants.

- The outpatient phase:

Participants will be treated with either SZC, as per local label, or SoC, as per local practice for 180 days.

Visits will occur 7, 30, 60, 90, 120, 150, 180 (end of treatment [EOT]) days after discharge visit (randomisation). Only visits at 7, 90, and 180 days will be on-site visits: the remaining being telephone visits.

- The follow-up phase:

A follow-up site visit (end of study visit) will occur approximately 7 days after EOT.

Data will be collected at on-site visits, via telephone visits and medical chart reviews.

The study will be conducted in approximately 30 to 50 sites in 4 to 7 countries in Europe.

Disclosure Statement: This is a parallel-group treatment study with 2 treatment arms that are open label.

Masking: No masking

Number of Participants:

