6.7 Concomitant Therapy

Sodium zirconium cyclosilicate can transiently increase gastric pH by absorbing hydrogen ions that can lead to changes in solubility and absorption kinetics for co-administrated drugs with pH-dependent bioavailability. Therefore, SZC should be administered at least 2 hours before or 2 hours after oral medications with gastric pH-dependent bioavailability.

Examples of drugs that should be taken 2 hours before or after SZC to avoid possible raised gastric pH drug interaction are listed below:

Class of Drug	Drugs
Aazole antifungals	Ketoconazole, itraconazole, posaconazole
Anti-human immunodeficiency drugs	Atazanavir, nelfinavir, indinavir, ritonavir, saquinavir, raltegravir, ledipasvir, rilpivirine
Tyrosine kinase inhibitors	Erlotinib, dasatinib, nilotinib

Note, this list is not exhaustive. Please refer to the SmPC of concomitant medications the participant gets administered for pH dependent bioavailability.

Sodium zirconium cyclosilicate can be co-administered with oral medications that do not exhibit pH-dependent bioavailability without spacing of dosing times.

In a drug-drug interaction study in healthy volunteers, co-administration of S_ZC 15 g with tacrolimus 5 mg resulted in a decreased tacrolimus area under concentration curve and maximum observed plasma concentration by 37% and 29%, respectively. Therefore, tacrolimus should be taken at least 2 hours before or after S_ZC. In the same study, co-administration of S_ZC and cyclosporin did not show a clinically meaningful interaction.

Potassium binders will not be authorized in Arm A, unless they are prescribed as rescue therapy (see Section 6.7.1).

Any medication or vaccine (including over-the-counter or prescription medicines, vitamins, and/or herbal supplements) or other specific categories of interest that the participant is receiving at the time of enrolment or receives during the study must be recorded along with:

- Reason for use
- Dates of administration including start and end dates
- Dosage information including dose and frequency.

If the participant received one (or more) Coronavirus disease 2019 (COVID-19) vaccination(s) prior to enrolment, then this needs to be recorded in the eCRF.

The sponsor or contract research organization study physician should be contacted if there are any questions regarding concomitant or prior therapy.

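### The RAASi-use rule for Exploratory Endpoint #17 loses a continuous user whose only RAASi record is replaced on the reference day, and its dose comparison names no frequency

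*SAP*

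**What the plan says.** SAP 4.2.25.2 derives RAASi use from concomitant medication records. A participant is on RAASi at discharge if one or more records satisfy "Start Date is prior to the date of randomisation and End Date is ongoing or after the date of randomisation". Day 90 has the same form, "Start Date is prior to day 90 post-discharge and End Date is ongoing or after day 90 post-discharge", and so does Day 180.

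The Protocol Synopsis puts randomisation and discharge on the same day: "The day they get discharged from the hospital, participants will be randomised to one of the 2 parallel arms at this visit".

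A dose decrease is defined "where CMDECOD at 90 or 180 days matches that at discharge but the CMDOSTXT is less than at discharge". For the same drug, an increase is the mirror image on CMDOSTXT. Protocol 6.7 requires each medication to be recorded with start and end dates and "Dosage information including dose and frequency". The SAP comparison uses no frequency term and does not define what CMDOSTXT contains.

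SAP 4.2.25.1 lists four summaries at 90 and 180 days: remained on, increased, decreased and initiated. The first three are restricted to participants on RAASi at discharge. SAP 4.2.25.2 gives no derivation for the fourth.

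**The concern.** The objective behind this endpoint is the ability to continue RAASi. Discharge is a day on which a prescription may be rewritten, and it is also the reference day for the status rule. With a strict limit on each side, two adjoining records that meet on that day both fail, so someone who never stopped treatment is recorded as untreated. The denominators of three summaries would then omit people the endpoint is meant to describe, and the fourth summary could count them as new users.

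The dose rule raises a separate question. If it compares amounts per intake rather than per day, it can miss a reduction or report an increase that did not occur.

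**Working it through.** The plan states no figure for this point, so there is none to reproduce. The check applies the rule as written to possible record patterns.

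**Notation.** Offset 0 is the randomisation and discharge date (SAP 3.3.1 calls this Day 1 of the outpatient phase; the offset is only for convenience). A record has start S and end E.

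- SAP rule at reference day r: on if any record has S < r and (E ongoing or E > r).
- Inclusive-start rule: on if any record has S ≤ r and (E ongoing or E > r).

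| RAASi records | Discharge, SAP rule | Discharge, inclusive start | Day 90, SAP rule | Day 180, SAP rule |
|---|---|---|---|---|
| One record, −30 to ongoing | on | on | on | on |
| −30 to 0; new dose 0 to ongoing | **not on** | on | on | on |
| −30 to −1; new dose 0 to ongoing | **not on** | on | on | on |
| −30 to 0; new dose +1 to ongoing | **not on** | **not on** | on | on |
| First start on 0 | not on | on | on | on |
| −30 to −5; restart on 0 | not on | on | on | on |
| −30 to 0, no replacement | not on | not on | not on | not on |
| Replaced on 0, second RAASi unchanged | on | on | on | on |
| −30 to 90; new dose 90 to ongoing | on | on | **not on** | on |

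In row 2, the old record fails because 0 > 0 is false and the new one fails because 0 < 0 is false. The strict end limit is reasonable taken alone (row 7). The loss comes from combining it with a strict start limit. Row 4 shows that an inclusive start is not sufficient: a replacement dated the next day also has to be joined. In the last row, the inclusive start gives on at Day 90, because 90 ≤ 90.

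A row 2 participant is off at discharge and on at Day 90. With no derivation for initiation, the natural reading counts that participant as an initiation.

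**Dose comparison**, same drug, illustrative units, assuming CMDOSTXT holds the amount only:

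- 5 twice daily to 5 once daily. Amount: 5 against 5, so no change. Daily dose: 5 × 2 = 10 against 5 × 1 = 5, a decrease.
- 5 twice daily to 10 once daily. Amount: 10 > 5, so an increase. Daily dose: 5 × 2 = 10 against 10 × 1 = 10, no change.

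If CMDOSTXT instead includes frequency as text, greater and less are not well defined on it. Under either reading the SAP needs to name the quantity compared. The increase rule also has a first limb that classes any change of drug name as an increase ("A RAASI dose increase at 90 and 180 days post-discharge is defined where the CMDECOD at discharge is different at 90 or 180 days"), so the handling of switches needs stating at the same time.

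**The case against.** Several points on the other side stand.

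- **A first start on the randomisation day is not clearly misclassified.** SAP 3.3.1.2 ends the inpatient period before the randomisation date and begins the outpatient period on it. Under that convention a RAASi first taken that day is an outpatient start. A reader might call all such cases false initiations; the documents do not support that.
- **An inclusive start has a price.** The study is open label, and dates alone cannot show whether a same-day change came before or after allocation was known. Counting the new record at discharge makes its dose the reference, so a discharge-day reduction would never appear as a decrease. Keeping the strict start and allowing an end on or after the reference day would also recover row 2 with a pre-randomisation reference. It would, however, count a RAASi stopped that day as on, and it would not recover row 3. This is a choice the SAP should state.
- **Not every discharge-day change is affected.** One other qualifying record keeps the participant on, and the gap needs old and new doses to be separate records. The SAP's own dose comparison presupposes separate records, but no eCRF convention is visible.
- **The frequency point is conditional.** Protocol 6.7 shows that frequency is collected; it does not show that CMDOSTXT excludes it.
- **The Day 90 and Day 180 case is narrow.** It needs a record change dated exactly on that day.

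None of these removes the same-day replacement gap. No other section supplies a rule that closes it.

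**Conclusion.** The point holds in a limited form and is minor. Read literally, SAP 4.2.25.2 gives the wrong status to a continuous user whose only RAASi record is replaced on a reference day. It also leaves the dose quantity undefined, with wrong classifications if CMDOSTXT is the amount alone.

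Three stronger inferences are not supported:

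- **A headcount.** One could assume that 60% of the 130 planned randomised participants use a RAASi (130 × 0.60 = 78) and that 10% to 30% of them have it changed at discharge (about 8 to 23). Neither rate is in the documents, so the number affected cannot be derived.
- **An effect on the main results.** Protocol 4.2 and Appendix A 5 assign RAASi down-titration and discontinuation events to the adjudication committee. The primary endpoint and the RAASi secondary endpoint therefore do not rest on this derivation. Endpoint #17 is descriptive and outside the testing hierarchy, so power and alpha are unaffected.
- **Bias between arms.** Protocol 2.2 describes reducing potassium-raising medication as common practice, and allocation is open. More same-day reductions under SoC are therefore conceivable, but nothing in the documents measures this.

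**What to change.** Amend SAP 4.2.25.2 as follows:

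1. Define use at discharge, Day 90 and Day 180 as Start Date on or before the reference day and End Date ongoing or after it.
2. Treat a replacement record starting on the same day or the next day as continuous use.
3. State which record supplies the reference dose at discharge when a change is dated that day, given that allocation is open label.
4. State whether a RAASi first started on the randomisation day counts as on at discharge or as initiated, and add the missing derivation for initiated.
5. Compare total daily dose (dose × frequency) within the same drug, and say how drug switches are reported.

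The cost is SAP wording and a small programming change. Protocol 6.7 already requires dates, dose and frequency, so no new data collection is needed. The programmer should confirm how CMDOSTXT and frequency are stored before item 5 is coded.

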This exploratory endpoint will descriptively summarise the use of RAASi in each treatment arm. This will include, but need not be limited to: frequency (%) of participants on RAASi at discharge who remained on RAASi at 90 and 180 days post-discharge, respectively; frequency (%) of participants on RAASi at discharge who have increased RAASi dose by 90 and 180 days post-discharge, respectively; frequency (%) of participants on RAASi at discharge who have decreased RAASi dose by 90 and 180 days post-discharge, respectively; frequency (%) of participants who initiated RAASi by 90 and 180 days post-discharge, respectively.

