#### **4.2.25.3 Handling of Dropouts and Missing Data**

Participants who experience all-cause death, or loss to follow-up prior to days 90 and 180 respectively will be excluded from the numerator and denominator of the analysis.

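### In exploratory endpoint #17, any change of RAASi drug counts as a dose increase whatever the dose, and a decrease is possible only on the same drug

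*SAP*

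**What the plan says.** SAP 4.2.25.2 gives the increase definition in two limbs. The first says that an increase "is defined where the CMDECOD at discharge is different at 90 or 180 days". The second is "or where CMDECOD at 90 or 180 matches that at discharge but the CMDOSTXT is greater than at discharge". A decrease has one limb only: "where CMDECOD at 90 or 180 days matches that at discharge but the CMDOSTXT is less than at discharge". Here CMDECOD is the coded drug name and CMDOSTXT the recorded dose.

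The same section identifies RAASi use at Day 90 by a medication record for which "Start Date is prior to day 90 post-discharge and End Date is ongoing or after day 90 post-discharge", with the same logic at Day 180.

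SAP 4.2.25.1 sets the population for the increase row: "The number and proportion of participants on RAASI at discharge who have increased RAASI dose by 90 and 180 days post-discharge, respectively, by treatment arm". SAP 4.2.25.3 gives the only exclusions: "Participants who experience all-cause death, or loss to follow-up prior to days 90 and 180 respectively will be excluded from the numerator and denominator of" this summary.

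Protocol 9.4.3.3, endpoint #17, asks for four summaries: participants who remained on RAASi, those with an increased dose, those "who have decreased RAASi dose by 90 and 180 days post-discharge", and those who started RAASi. It does not equate a change of drug with an increase in dose. SAP section 2, which lists departures from the protocol's planned analyses, does not mention one here.

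**The concern.** The first limb of the increase definition contains no dose comparison, no rule for equivalence between drugs, and no condition that the new regimen is stronger. The decrease definition excludes every change of drug. The two rules are therefore not mirror images: a change of drug can enter only the favourable row.

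The stated objective of endpoint #17 is the ability to continue RAASi, so readers will take the increase row as a sign of success and the decrease row as a sign of failure. The error need not be equal between arms. Protocol 9.2.1 expects RAASi down-titration to reduce response in the SoC arm relative to SZC. If part of that takes the form of switches to a weaker drug, SoC would show more apparent increases, and the comparison would point the wrong way.

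**Working it through.** There is no stated figure to reproduce. The check applies the two rules literally to each kind of change, for a participant on RAASi at discharge who is neither dead nor lost to follow-up.

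| Change from discharge to Day 90/180 | Increase? | Decrease? |
|---|---|---|
| Same drug, higher dose | Yes | No |
| Same drug, lower dose | No | Yes |
| Same drug, same dose | No | No |
| Switch, equivalent dose | Yes | No |
| Switch, weaker regimen | Yes | No |
| Complete stop, absent name read as different | Yes | No |
| Complete stop, a RAASi record required at that day | No | No |

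**Switches.** The two switch rows need no interpretation. The coded name differs, so the first limb is met whatever the dose, and the decrease rule fails because the name does not match.

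**Complete stops.** A participant who stopped has no qualifying record at Day 90 or 180 but stays in the population, since only death and loss to follow-up remove people. Whether an absent name is different from the discharge name is not stated. Either way a stop is not a decrease.

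**Loss of one of several drugs.** SAP 4.2.25.2 allows one or more RAASi at discharge but does not say whether comparison is per participant or per record. Compared per participant, two drugs at discharge and one later is a difference, and so an increase. Compared per record, the retained drug still matches and is judged on its own dose.

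**Size.** Let n be the evaluated RAASi users in an arm, e the switches to an equivalent regimen, w the switches to a weaker one, and d the complete stops. Setting aside multi-drug regimens:

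- Overstatement of the increase row = (e + w)/n at least, and (e + w + d)/n if an absent name counts as different.
- Understatement of the decrease row = w/n for switches on every reading. Stops also add nothing to it.

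The documents give none of n, e, w or d. The protocol plans about 130 randomised, so about 130/2 = 65 per arm and n is at most about 65. One misclassified participant then moves the row by at least 1/65 = 1.5 percentage points.

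As an illustration only, assume n = 40 and 10 participants who either switch to a weaker drug or stop:

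- All 10 switch: 10/40 = 25 points too many increases on either reading, and 25 points missing from decreases.
- All 10 stop: 10/40 = 25 points too many increases if absence counts as different, 0/40 = 0 if it does not. None appears as a decrease, and the row for those who remained on RAASi falls by 25 points.
- If k of the 10 switch and the rest stop, the overstatement lies between k/40 and 10/40.

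**The case against.** The strongest reply is that little depends on this table. Endpoint #17 is exploratory, descriptive and outside the testing order in SAP Table 5. Its central question, whether participants stay on RAASi, is answered by the row for those who remained on RAASi and by the count in SAP 4.2.25.4. Neither uses the increase and decrease rules. All of this stands, and it limits the size of the point. It does not rescue the two affected rows: a switch leaves the participant on RAASi, so the remained row cannot reveal that the increase row is wrong.

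A reader might infer three stronger things, which the documents do not support:

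- **That the SAP rules a complete stop to be an increase.** It does not say so. The section first defines use at each day by an active record, and one can fairly hold that without a record there is no drug name to compare. The defect is that the text leaves the matter open.
- **That losing one of two RAASi drugs is always an increase and never a decrease.** This depends on the unstated unit of comparison. Under a per-record comparison a lower dose of the retained drug would be a decrease.
- **That the rule undermines the down-titration results.** Protocol 4.2 and Appendix A 5 give the determination of RAASi down-titration and discontinuation events to the blinded adjudication committee. The primary endpoint and the RAASi secondary endpoint do not use the SAP 4.2.25.2 derivation. What can happen is that one participant is an adjudicated down-titration in those analyses and an increase in the #17 table. That is an inconsistency in reporting, not an error in the adjudicated result.

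**Conclusion.** The point holds for drug switches without any assumption: as written, every change of coded RAASi drug is an increase and none can be a decrease, which is not what the protocol asks to have counted. For complete stops and lost components the text is open, and an increase is one permitted result. That a complete stop is never a decrease holds on every reading.

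The effect is at least (e + w)/n on the increase row in each arm. It cannot be put as a single figure, because the documents give no switch or stop rates; the 25-point illustration rests wholly on the assumed 10 of 40. No p-value, primary or secondary estimate, or confirmatory conclusion changes. The rows should still be corrected, because they can report an unfavourable change as a favourable one.

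**What to change.** Amend SAP 4.2.25.2 as follows:

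- Delete the limb that makes a different drug name an increase.
- Define increase and decrease by numeric total daily dose of the same drug. CMDOSTXT appears from its name to be a text field (an assumption). If so, it must be converted first, because as text 10 sorts below 5.
- Report drug switches as a separate category.
- Report complete discontinuation and loss of a RAASi component explicitly as discontinuation or reduction, never as an increase, and consistently with the adjudicated down-titration (including discontinuation) events.
- State whether participants on several RAASi drugs are compared per participant or per drug.

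Adjudication cannot replace this derivation, because for RAASi the committee determines only down-titration and discontinuation and does not identify increases. It can serve as a check on the reduction categories. If a stop appears both as discontinuation and as a fall in the remained row, a footnote should say that the rows overlap.

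The cost is SAP wording and minor programming. Protocol 6.7 already requires dose, frequency and dates for every medication, so no new data are needed.
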